Note to authors – this template is a guide – all the sections below must be included however this is not exhaustive, other sections may be added. Don't forget to delete the blue "guides" from each section! Once your protocol content is complete, update the index by clicking in the left of the field and pressing F9

# 2. Study Synopsis

TITLE OF CLINICAL TRIAL:	fMRI Neurofeedback as a novel neurotherapy for children with ADHD				
Protocol Short Title/ Acronym:	AFNIS				
Study Phase If Not Mentioned In Title:	Proof of concept randomised controlled trial				
Sponsor Name:	King's College London, South London and Maudsley Trust				
Chief Investigator:	[name]				
UKCRN Number:					
REC Number:	230303				
Medical Condition Or Disease Under Investigation:	Attention Deficit Hyperactivity Disorder (ADHD)				
Purpose Of Clinical Trial:	Powered proof of concept experimental randomized placebo-controlled double-blind trial to test the mechanism and clinical efficacy of real-time fMRI neurofeedback (fMRI-NF) of right inferior frontal cortex (rIFC) compared to sham fMRI-NF in ADHD children				
Primary Objective:	To examine whether fMRI neurofeedback of right frontal cortex (rIFC) in ADHD children will 1) reduce their ADHD symptoms				

	
 
increase activation in rIFC over the 14 sessions
 
			
Secondary Objective(s):	
 
To test whether the fMRI neurofeedback will : 
 
improve other clinical ADHD severity measures
 
improve performance on a battery of cognitive tasks relevant to ADHD
 
will increase activation in rIFC in a Stop fMRI task
 
Will increase the activation of an entire functional network connected with the rIFC
 
has no side effects
 
will improve clinical and cognitive measures longer-term, 6 months after training
 

			
Trial Design:	Randomised controlled double-blind trial			
Endpoints:	
 
Performance on a cognitive task battery of cognitive control tasks
 
Parent ratings on the ADHD Rating scale
 
			
Sample Size:	100 ADHD children, 10-18 years			
Summary Of Eligibility Criteria:	Meeting clinical diagnosis for Attention-Deficit Hyperactivity Disorder (ADHD); male; age range 10- 18 years; stable medication or non-medicated; no comorbid conditions other than oppositional defiant and conduct disorder; IQ > 80.			
Intervention (Description, frequency, details of delivery)	Participants will undergo four hourly fMRI scans with feedback of their activation of rIFC. They will be asked to modulate this activation via a video-game that is connected to the activity of the rIFC.			
Comparator Intervention:	Sham real-time fMRI neurofeedback			
Maximum Duration Of Treatment Of A Subject:	2 weeks			
Version And Date Of Final Protocol:	Version 2 27/10/2017			
Version And Date Of Protocol Amendments:				

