# 7.1.2 Secondary endpoints

- 1) The ADHD Index of the Conners Parent Rating Scales (CPRS).
- 2) Stop fMRI task performance and related brain activation.
- 3) A cognitive task battery we have developed for ADHD that measures key functions including inhibition, attention, timing and motivation and which lasts 30min (Rubia, Smith, & Taylor, 2007).
- 4) Other clinical measures:
  - a. the Affective Reactivity index (ARI) (Stringaris et al., 2012) (2min)

- b. the Columbia Impairment Scale (CIS) (Bird, et al., 1003) (5min)
- c. The Mind excessive wandering scale (MEWS) (Mowlem et al., 2016)
- 4) Side effect scale (Hill & Taylor, 2001). (5min)

5) Long-term effects will be assessed 6 months after training in the primary outcome measure (ADHD-RS for parent-ratings), the ARI, the MEWS and in the performance on the cognitive task battery.

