# 7.2 Trial Design

Double-blind, parallel-group, randomised placebo-controlled trial.

We will test the superiority of the real-time fMRI neurofeedback of rIFC over the sham-NF.

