# 13. Assessment of Safety

# 13.1 Specification, Timing and Recording of Safety Parameters.

MRI is considered safe and non-invasive and there are no side effects are usually recorded.

We will measure side effects before and after the treatment as well as adverse effects. However, we do not expect any side or adverse effects as the methodology is safe in children and we found no side or adverse effects in our pilot study.

However, there is a slight risk that the scanner is sometimes perceived as unpleasant and uncomfortable. The researchers will be sensitive to this possibility and will suspend testing sessions at the request of the participant or at the first signs of distress and discomfort. The participant will be informed that he/she is free to terminate the scanning session whenever he/she wants to. Alerting mechanisms ensure easy communication and radiographers will constantly check that the participant is content to remain in the scanner.

Adolescents are sometimes anxious about the scanner – they will be shown the "mock scanner" to familiarise them with the scanner beforehand and they will be able to tell in the first scan whether they are happy to be scanned 4 times. Every effort will be made to ensure that they do not feel anxious or claustrophobic. However, if they feel that the scanner is frightening to them, they will not have to participate. The same applies for adolescents who feel claustrophobic in the scanner.

The scanner is also noisy and this may be unpleasant for some children. We will therefore expose them to the noise beforehand in the mock scanner. If the children feel that they dislike the noise, they do not have to participate. Also, in order to minimize the discomfort of the noise, we will provide all participants with headphones that are specifically designed for MRI scanners to reduce the noise level. This is standard procedure for all scanning subjects at the IOP.

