# 14.1 Sample Size

100 ADHD adolescents will be enrolled in the study, randomised into the fMRI-NF of rIFC (N = 50) and the sham NF (N = 50).

The estimates of a clinically relevant effect size were calculated from our IOPPN pilot study on fMRI-NF in ADHD adolescents using the exact same outcome measures. ES for clinical efficacy in our pilot study was around 0.6. For a mean ES of 0.6 and a power of 80% with a p < 0.05, we would need 45 children in each group. We hence powered the study to include 50 children in each group accounting for a generously estimated potential drop-out rate of up to 10%. Our pilot study was well tolerated by ADHD children who liked the Neurofeedback "game" and we had a drop-out rate of only 5%, which is lower than the 6-10% drop-out rate we have had for studies of repeated fMRI scans under several medication conditions.

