#### 14.3 Analysis

A description of the statistical methods to be employed, including timing of any planned interim analyses should also be provided The level of significance that is to be used in each trial analysis must be stipulated, together with the procedure(s) for accounting for any missing, unused, and spurious data. Procedures for reporting any deviation from the original statistical plan should be described and justified. The data set for any analysis must be clearly stipulated (e.g. "all subjects", "randomised subjects", "intent to treat") and the population(s) should be clearly defined. Define the trial stopping rules if appropriate.

For all analyses, repeated measures ANOVAs will be conducted with TIME as within-subject factor and GROUP as between subject factor. Supplementary analyses may include parametric correlation analyses (for example Pearson's correlation tests).

The named researchers have substantial and proven experience in these types of analyses, having published and taught extensively.

For missing data, imputations will be used. The individual estimates from the multiply-imputed datasets will then be used to calculate a combined estimate by applying Rubin's Rules [Little and Rubin, 2002].

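### The objective of showing no side effects is paired with a test of difference, which cannot show absence; an estimate with a confidence interval should replace it

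*Protocol*

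**What the plan says.** The secondary objectives in the Protocol synopsis (section 2) open with "To test whether the fMRI neurofeedback will", and the fifth item is that it "has no side effects".

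Section 7.1.2 lists a "Side effect scale" among the secondary endpoints. Section 13.1 gives the timing: "We will measure side effects before and after the treatment as well as adverse effects". The same section states the expectation: "we do not expect any side or adverse effects as the methodology is safe in children".

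Section 14.3 fixes the method: "For all analyses, repeated measures ANOVAs will be conducted with TIME as within-subject factor and GROUP as between subject factor". It makes no exception for side effects. The sample size in section 14.1 rests on clinical efficacy alone, at "a power of 80% with a p < 0.05". The Protocol states no margin, tolerated rate or confidence-interval criterion for side effects.

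**The concern.** A repeated measures ANOVA tests whether the arms differ, or whether scores change. It can give evidence that side effects exist. It cannot give evidence that they do not, because a non-significant result also arises when a real effect is too small for the sample to detect. Here the objective is worded as absence, so non-significance is the only result that could count in its favour.

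The participants are boys aged 10 to 18, and the background section argues for the therapy partly because it is expected to be free of side effects. An analysis that cannot support that conclusion should not be the one attached to it.

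A second, smaller point concerns the comparison. Both arms undergo the same scanning. The contrast between arms isolates effects of contingent feedback, which suits the objective, but harm common to both arms cancels out of it.

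**Working it through.** **1. The plan's own figure.** Inputs from section 14.1: effect size 0.6, 80% power, p < 0.05. A two-sided, two-sample t calculation gives 44.6 per arm, so 45. Allowing for 10% drop-out, 45 / 0.9 = 50. Both stated figures reproduce. They concern efficacy; the checks below ask what the same sample can say about side effects.

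**2. Assumptions.** The Protocol gives no SD, relevant difference or pre-post correlation for the side effect scale. Differences are therefore in units of the cross-sectional SD, taken as equal in both arms and at both times. With one measurement before and one after treatment, the TIME-by-GROUP test equals a two-sample t test on change scores. The SD of a change score is sqrt(2(1 − r)), where r is the pre-post correlation. At r = 0.5 it is sqrt(2 × 0.5) = 1.

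**3. Power at 45 per arm, two-sided 0.05, r = 0.5.**

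| True increase (SD) | Power | Chance of non-significance |
|---|---|---|
| 0.2 | 16% | 84% |
| 0.3 | 29% | 71% |
| 0.4 | 47% | 53% |
| 0.5 | 65% | 35% |

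**4. Dependence on the correlation, for a true increase of 0.3 SD.** The 95% CI half-width is t(0.975, 88 df) × SD of change × sqrt(2/45), where 1.987 × sqrt(2/45) = 0.419.

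| r | SD of change | Chance of missing 0.3 SD | 95% CI half-width |
|---|---|---|---|
| 0.3 | sqrt(1.4) = 1.183 | 78% | 0.419 × 1.183 = 0.50 SD |
| 0.5 | 1.000 | 71% | 0.42 SD |
| 0.7 | sqrt(0.6) = 0.775 | 56% | 0.419 × 0.775 = 0.32 SD |

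**5. Baseline-adjusted estimate.** Adjusting for the baseline score gives a residual SD of sqrt(1 − r²), which is 0.954 at r = 0.3 and 0.714 at r = 0.7. The half-width becomes 0.419 × 0.954 = 0.40 SD and 0.419 × 0.714 = 0.30 SD. The chance of missing 0.3 SD becomes 69% and 50%. This is more precise than the change-score analysis at both values, but still far from showing absence.

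**6. What a formal claim of absence would need.** For one-sided non-inferiority (alpha 0.025, 80% power, SD 1, no true difference), the smallest margin at 45 per arm is (1.96 + 0.84) × sqrt(2/45) = 0.59 SD. A margin of 0.3 SD would need 175 per arm before drop-out.

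**7. Adverse events, for illustration only.** If no events occur in n children, the exact two-sided 95% upper limit for the true rate is 1 − 0.025^(1/n). For n = 50 this is 7.1%; for n = 45 it is 7.9%.

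**The case against.** The strongest objection is that the Protocol nowhere says how a non-significant side-effect result will be read. A reader might infer that p > 0.05 will be declared proof of safety. That is an inference from the objective and the method, and no sentence states it. The expectation of no side effects in section 13.1 is a prior belief linked to the pilot study and sets no analysis rule. This objection stands. It leaves the mismatch between objective and method in place, because the wording and the blanket ANOVA rule are both in the text.

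A reader might also invoke section 7.2, "We will test the superiority of the real-time fMRI neurofeedback of rIFC over the sham-NF", as if side effects were to be judged by a superiority test. That sentence does not mention side effects, and the ANOVA tests for a difference in either direction.

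On shared scanning, it would go too far to say that the ANOVA is blind to harm common to both arms. Its TIME effect would show a shared change in scale score, although without a control. Sham is also the right comparator for effects specific to neurofeedback.

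Adverse-event counts are not clearly placed under the ANOVA rule. They appear in the safety section with no test assigned, so the zero-event limits illustrate what such counts could show and do not measure an error in the plan.

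Finally, an analysis plan that is not shown might add confidence intervals. That would help, but the objective and the blanket rule in the Protocol would still need correcting.

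**Conclusion.** The point holds as a mismatch between a stated objective and its stated method. The Protocol sets out to test for absence of side effects and assigns a difference test that cannot show it. At this sample size, non-significance would be the more likely result for a true increase of up to about 0.4 SD at r = 0.5. For an increase of 0.3 SD, the chance of missing it is 56% to 78% over correlations from 0.7 to 0.3. These figures rest on assumed SD units, equal variances and 45 analysed per arm.

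The point concerns one secondary objective. The primary analysis, the sample size and the data collected are unaffected. The change should be made, but the trial does not depend on it.

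**What to change.** 1. In the synopsis, reword the objective as estimating the side effects of neurofeedback.
2. In section 14.3, exempt the side effect scale from the rule that applies ANOVA to every analysis. Report the baseline-adjusted active-minus-sham difference with its 95% CI.
3. Limit the conclusion to what the interval excludes, that is, effects above the upper confidence limit. If absence of a relevant effect is to be claimed, set and justify a margin in advance.
4. Because both arms have the same scanning, also report the number of children with any adverse event, by arm and overall, with exact 95% CIs.

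The cost is a change of wording in two places. No further data or participants are needed. The downside is a more cautious safety claim.

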#### 7.1.1 Primary endpoints

1) ADHD symptoms as measured on the ADHD-Rating Scale (ADHD-RS). (Dupaul et al. 1999).

2) Monotonic increase in inferior frontal lobe activation across the 14 neurofeedback sessions in the active group.

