# **12. Assessment of Efficacy**

The ADHD Rating scale is the primary efficacy measure which is a standard measure used in ADHD to measure effects of pharmacological and non-pharmacological treatment. The ADHD index of the Conners Parent Rating Scale is a commonly used secondary efficacy measure for behavioural improvement in ADHD.

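### The protocol is inconsistent on whether it has one primary endpoint or two, and its single-comparison sample size supports the powered claim for clinical efficacy only

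*Protocol*

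**What the plan says.** The statements on the primary endpoint, in document order:

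- **Section 2, Primary Objective row:** two aims, fewer ADHD symptoms and more rIFC activation over the sessions. The Secondary Objectives row of the same table includes the cognitive tasks.
- **Section 2, Endpoints row:** two items, neither labelled primary. The first is "Performance on a cognitive task battery of cognitive control tasks"; the second is the parent-rated ADHD-RS. rIFC activation is absent.
- **Section 7.1.1, Primary endpoints:** the ADHD-RS, and "Monotonic increase in inferior frontal lobe activation across the 14 neurofeedback sessions in the active group".
- **Section 7.1.2, Secondary endpoints:** item 3 is "A cognitive task battery we have developed for ADHD that measures key functions including inhibition, attention, timing and motivation". Item 5 refers to the primary outcome measure in the singular and identifies it as the parent-rated ADHD-RS.
- **Section 12:** "The ADHD Rating scale is the primary efficacy measure". Section 12.1 lists nothing else.

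On size, Section 14.1 takes an effect size of about 0.6 for clinical efficacy from the pilot and states: "For a mean ES of 0.6 and a power of 80% with a p < 0.05, we would need 45 children in each group". It then enrols 50 per group to allow for up to 10% drop-out. The synopsis (Purpose row) and the objectives paragraph of Section 7.1 describe the trial as powered to test both mechanism and clinical efficacy. Section 7.2 states a superiority test against sham, and Section 14.3 prescribes a TIME by GROUP repeated measures ANOVA for all analyses.

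**The concern.** The primary endpoint fixes what the trial may conclude. Here a reader cannot tell whether there is one primary or two, and the synopsis puts a secondary measure at the head of its endpoint list. A result on either listed primary could later be presented as the trial's main finding, with a section of the protocol to cite for it.

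The sample size rests on one effect size, for one endpoint, at one significance level. If rIFC activation is a second primary, the protocol gives no effect size or power for it, yet calls the trial powered for mechanism.

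The second primary has a further problem. A rise in the active arm alone makes no use of the sham arm, although Section 6 gives the missing sham control as the reason why the pilot could not rule out placebo effects.

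**Working it through.** **Inputs.** From Section 14.1: effect size d = 0.6 (clinical efficacy), "a power of 80% with a p < 0.05", 45 per arm, 10% drop-out. From Section 14.2: 1:1 allocation. Sidedness is not stated. Two-sided is assumed because it reproduces the plan's figure; a one-sided 5% test would need only 35 to 36 per arm.

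**Step 1: the plan's own figure.** Two-sample t test, noncentrality d × √(n/2) = 0.6 × √22.5 = 2.846 with 88 degrees of freedom. Power is 80.4% at 45 per arm and 79.5% at 44, so 45 is the smallest adequate number. Drop-out: 45 / 0.90 = 50. Section 14.1 is reproduced.

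**Step 2: two primaries under each possible success rule.** No effect size is given for rIFC activation, so d = 0.6 in an active-versus-sham comparison is assumed for it as well. The correlation ρ between the two test statistics is unknown and is varied from 0 to 0.9.

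*(a) Either endpoint suffices, each at 5%.* If independent, familywise error = 1 − 0.95² = 9.75%. From the bivariate normal distribution it is 9.1% at ρ = 0.5 and 7.0% at ρ = 0.9. Power for ADHD-RS stays at 80.4%.

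*(b) Alpha split, 2.5% each.* Error is held at 5%. Power per endpoint from the same t test is 71.4% at 45 per arm and 76.4% at 50. Reaching 80% needs 55 evaluable per arm; 55 / 0.90 = 61.1, so 62 enrolled.

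*(c) Both required, each at 5%.* Error is at most 5%. Joint power at 45 per arm:

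| ρ | Joint power |
|---|---|
| 0 | 0.804² = 64.6% |
| 0.5 | 69.2% |
| 0.9 | 75.4% |

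The correlated values use a bivariate normal with each margin set to 80.4%. If independent, 80% joint power needs 59 evaluable per arm (0.898² = 80.7%; 58 gives 79.8%); 59 / 0.90 = 65.6, so 66 enrolled.

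*(d) Fixed sequence, ADHD-RS first at 5%, rIFC activation only if ADHD-RS is significant.* Familywise error is held at 5%, power for ADHD-RS stays at 80.4%, and 45 per arm stands.

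**Step 3: the second primary against the design.** Section 7.1.1 defines it in the active arm only. Section 7.2 asks for superiority over sham, and Section 14.3 applies TIME by GROUP to everything. A within-arm trend contains no GROUP contrast, so it can neither show superiority nor be the analysis that 14.3 prescribes.

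**The case against.** A good part of the case on the other side stands.

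- **A reader might infer a third primary, the cognitive battery.** The documents do not support that. The synopsis row is headed as endpoints, not primary endpoints, and both the Secondary Objectives row and Section 7.1.2 class the battery as secondary. The row is out of step and needs correcting, but it gives no ground for counting battery scores in the familywise error.
- **A reader might infer that Section 14.1 is wrong, or that error and power both fail.** Neither follows. Section 14.1 describes one clinical comparison and is correct for it. Under rule (a) error rises and power does not fall; under (b) and (c) error is held and power falls.
- **Section 12 concerns efficacy, so it may name only the clinical primary and leave out the mechanistic one.** This is a fair reading of Sections 12 and 12.1 alone. It does not explain the singular primary outcome in Section 7.1.2 item 5, or the missing rIFC endpoint in the synopsis row.
- **A multiplicity rule may sit in a statistical analysis plan that is not shown.** True, and its absence here is not the point. But a later plan would inherit a protocol that disagrees on the number of primaries, and a sample size already fixed for one comparison.
- **The 10% drop-out may not occur.** At 50 evaluable per arm, joint power under rule (c) is 71.2% at ρ = 0 (0.844²) and 80.1% at ρ = 0.9. The shortfall would then be smaller, and absent at very high correlation.

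**Conclusion.** The inconsistency is real: two primaries in Section 7.1.1 and the synopsis Primary Objective, one in Section 7.1.2 item 5 and Sections 12 and 12.1, and a synopsis endpoint list that matches neither. ADHD-RS is the only measure common to all of them.

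Section 14.1 is sound for ADHD-RS but cannot carry the statement that the trial is powered for mechanism too. If both endpoints stay primary without a fixed order, the cost at 45 per arm is one of three: familywise error of about 7.0% to 9.75%, power per endpoint of 71%, or joint power of about 65% to 75%. These figures assume two-sided tests, and the power figures also assume d = 0.6 for an active-versus-sham rIFC comparison. The range over ρ shows how far they depend on the unknown correlation.

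Apart from any arithmetic, the second primary as defined cannot answer the trial's stated superiority question.

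**What to change.** 1. Name parent-rated ADHD-RS at the post-treatment assessment as the single primary endpoint in the synopsis, 7.1.1 and 12.1, tested two-sided at 5%. State that 14.1 covers this endpoint only.
2. Define rIFC activation as the active-versus-sham comparison (GROUP by session) and test it second in a fixed sequence, as the key mechanistic endpoint.
3. List the cognitive battery as secondary throughout, including the synopsis Endpoints row.
4. Limit the powered wording in the synopsis and Section 7.1 to clinical efficacy.
5. While editing, reconcile the session count behind the rIFC endpoint: 7.1.1 says 14, Section 6 says 15, and the visits in 8.1 add to 2 + 5 + 5 + 3 = 15.

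If the sponsor prefers two primaries, the protocol should state the success rule and the alpha for each, give an effect size for rIFC activation, and restate the power.

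**Cost.** No extra participants and no change to 14.1's number. It is more than a wording change, however: a declared primary moves down one level and changes from a within-arm to a between-arm comparison. rIFC activation could then no longer be a stand-alone confirmatory success if ADHD-RS misses.
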